#### 4.5. Prior and Concomitant Medications/Therapy

Prior and concomitant medications recorded during the study will be listed. These will be coded with the WHO Drug Dictionary (Version 201603 DDE).

Medications will be assigned as prior or concomitant based on the following rules:

- If both the start and stop date exist and are before the first dose date of study drug, the medication will be classified as a prior medication.
- If the start date is on or after the first dose date of study drug, the medication will be classified as a concomitant medication.
- If the start date is before the first dose date of study drug and the stop date is after the first dose date of study drug or the medication is ongoing, the medication will be classified as prior and concomitant.
- If the start date is missing and the stop date is before the first dose of study drug, the medication will be classified as prior.
- If the start date is missing and the stop date is after the first dose of study drug or the medication is ongoing, the medication will be classified as concomitant.
- If the start and stop dates are missing, the medication will be classified as concomitant.

## 4.6. Study Drug Exposure

### 4.6.1. Extent of Exposure

A listing of individual patient dosing data will be provided.

Study drug exposure will be summarized descriptively by cohort (Part 1) and by treatment group for each muscle (Part 2) for the safety population. Such summaries will include the total number of treatment doses, the number and percentage of patients with dose delay and reduction. If no patients experience dose delay and reduction, then no such summaries will be provided.

The total number of doses will be summarized by presenting the number and percentage of patients in each category. Categories refer to the total number of treatment doses. For Part 1, the possible values of the total number of treatment doses are: "1", "2", "3", "4", and "5". For Part 2 (double-blind period), the possible values of the total number of treatment doses over the course of the double-blind treatment period is: "1", "2", "3", "4", "5", "6", "7", "8", or "9". For Part 2 (open-label extension), the possible values of the total number of treatment doses over the course of the open-label extension is: "1", "2", "3", "4", "5", "6", "7", or "8".

The total study drug exposure in weeks will also be summarized and will be derived according to the following formula: Exposure (weeks) = [(Last dose date – First dose date) +21] / 7.

For Part 1, summaries of the total study drug exposure in weeks will be provided by cohort using descriptive statistics. The summary table will include a pooled summary across cohorts within each muscle treated.

For Part 2, summaries of the total study drug exposure in weeks will be provided by treatment group for each muscle treated. This will be done for the double-blind and open-label periods.

## 4.7. Efficacy Data

### 4.7.1. Variables

#### 4.7.1.1. Muscle Strength

Muscle strength variables consist of the following:

- Maximum (of 3 measurements) right ankle dorsiflexion MVIC
  - MVIC = maximum force (from 3 measurements) from the hand-held dynamometer
- Maximum (of 3 measurements) left ankle dorsiflexion MVIC
- (Part 2 only): MRC-MMT SCORE which represents the conversion of the MRC-MMT grade to the decimal version as follows: 5 = 5.0, 5- = 4.67, 4+ = 4.33, 4 = 4.0, 4- = 3.67, 3+ = 3.33, 3 = 3.0, 3- = 2.67, 2+ = 2.33, 2 = 2.0, 2- = 1.67, 1+ = 1.33, 1=1.0

For each of the muscle strength variables listed above, the absolute and percent change from baseline will be determined for each side (left, right) at each time point. In addition, the absolute and percent change from baseline will be determined for the average of the left and right sides at each time point.

#### 4.7.1.2. Motor Function

##### 10-Meter Walk/Run Test

- Time to complete 10-meter walk/run (seconds)

##### 6-Minute Walk Test

- Cumulative distance traveled at 1 minute (meters)
- Cumulative distance traveled at 2 minutes (meters)
- Cumulative distance traveled at 3 minutes (meters)
- Cumulative distance traveled at 4 minutes (meters)
- Cumulative distance traveled at 5 minutes (meters)
- Cumulative distance traveled at 6 minutes (meters)

##### 100-meter timed test (Part 2 open-label period only)

- Time to complete 100-meters (sec.)

##### Gait assessments

- General measures: Stride time (sec.), Stride length A (m), Stride length B (% height), Stride velocity A (m/s), Stride velocity B (height/s), Cadence (steps/min), Step length left (m), Step length right (m)
- Gait cycle phase measures: Swing left (%), Swing right (%), Stance left (%), Stance right (%), Double support initial right (%), Double support terminal left (%), Double support total (%)
- Gait assessment range of motion: Knee ROM left (deg.), Knee ROM right (deg.), Hip ROM left (deg.), Hip ROM right (deg.), Ankle ROM left (deg.), Ankle ROM right (deg.), Peak hip flexion angle in swing left (deg.), Peak hip flexion angle in swing right (deg.), Peak knee flexion angle in swing left (deg.), Peak knee flexion angle in swing right (deg.), Peak ankle flexion angle in swing left (deg.), Peak ankle flexion angle in swing right (deg.)
- Gait assessment foot drop: Mid-swing foot angle left (deg.), Mid-swing foot angle right (deg.)

For gait assessments reported on the left and right sides, the absolute and percent change from baseline will be determined for each side and then averaged. Should a patient have a gait assessment reported for one side (i.e. right side) but not the other side at an individual time point, the value for the average absolute (or percent) change from baseline for that patient and time point will be the absolute (or percent) change from the side from which the gait assessment was obtained.

##### Berg Balance Scale

- Total score from the 14 items on the instrument.

- The 14 items on the instrument are: Sitting to standing, Standing unsupported, Sitting with back unsupported but feet supported on floor or on a stool, Standing to sitting, Transfers, Standing unsupported with eyes closed, Standing unsupported with feet together, Reaching forward with outstretched arm while standing, Pick up object from the floor from a standing position, Turning to look behind over left and right shoulders while standing, Turn 360 degrees, Placing alternate foot on step or stool while standing unsupported, Standing unsupported one foot in front, and Standing on one leg.
- Each item score ranges from 0 to 4. The total score ranges from 0 to 56.

### **Falls (Part 2 double-blind and open-label)**

- Number of falls reported by patients wearing the PAMSys™ device
  - From Week 1 to Week 12 (3 months) [inclusive]
  - From Week 13 (3 months) up to Week 24 (6 months) [inclusive]
  - From Week 1 to Week 24 (6 months) [inclusive]
  - From Week 25 to Week 36 [inclusive]
  - From Week 37 to Week 40 [inclusive]
  - From Week 25 (6 months) to Week 48 (12 months) [inclusive]
  - From Week 1 up to Week 48 (12 months) [inclusive]
- Number of patients who fell at least once
  - From Week 1 to Week 12 (3 months) [inclusive]
  - From Week 13 (3 months) up to Week 24 (6 months) [inclusive]
  - From Week 1 to Week 24 (6 months) [inclusive]
  - From Week 25 to Week 36 [inclusive]
  - From Week 37 to Week 40 [inclusive]
  - From Week 25 (6 months) to Week 48 (12 months) [inclusive]
  - From Week 1 up to Week 48 (12 months) [inclusive]
- Risk of recurrent falls from Week 1 up to Week 24 (6 months)
- Risk of recurrent falls from Week 1 up to Week 48 (12 months)

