### **Falls**

Individual data on the number and type of falls recorded in 4-week time intervals along with details on the timing and classification of the individual falls recorded, per day, type of assistance, and information related to input (whether the fall was recorded by device detection or recorded by the individual patient) will be provided in a listing. This data will be included with the data collected in the double-blind placebo-controlled phase.

The number of falls as well as the number of patients who fell at least once occurring from Week 25 up to Week 48 inclusive will be summarized by treatment, including separate summaries for subintervals as outlined in [Section 4.7.1.2](#). A record of “Near-fall” will not be counted as a “Fall”.

Additional analyses may be performed as appropriate.

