### **Falls**

The hazard ratio of recurring falls between ACE-083 and placebo during the entire 12 months (excluding the screening interval) will be estimated using the Andersen-Gill recurrent events model with the following covariates: SEQUENCE, CMT-TYPE, PERIOD, and ankle dorsiflexion MRC-MMT decimal score where SEQUENCE refers to the treatment sequence from double-blind to open-label (ACE-083  $\rightarrow$  ACE-083 or Placebo  $\rightarrow$  ACE-083), and PERIOD

refers to the period of time of observation (“Double-blind”, “Open-label”). The “Double-Blind” period covers Weeks 1 to 24 and the “Open-label” period covers Weeks 25 to 48. The point estimate, p-value and 90% confidence interval for the hazard ratio for SEQUENCE will be provided.

Additional methods for the statistical analysis of the recurring event of falls may be considered and performed as appropriate (e.g. negative binomial regression with similar covariates as listed for the Andersen-Gill recurrent events model described above).

No multiple imputations will be performed for missing data.

The statistical analyses described above will be done on the Per Protocol Set and will be considered primary. The analyses described above will also be repeated for the Full Analysis Set.

Additional analyses may be performed as appropriate.

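### The last open-label falls window in SAP 4.7.1.2 is Weeks 37-40, so one descriptive quarter is 4 weeks long beside three of 12, and Weeks 41-48 belong to no quarter

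*SAP*

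**What the plan says.** SAP 4.7.1.2 (Motor Function, Falls) defines two falls variables for Part 2, the number of falls and the number of patients with at least one fall, each with the same list of windows. Three of the quarter-length entries are Weeks 1-12, 13-24 and 25-36. The fourth reads "From Week 37 to Week 40 [inclusive]".

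The same lists carry period totals for Weeks 1-24, Weeks 1-48 and the open-label phase. That last total is written as "From Week 25 (6 months) to Week 48 (12 months) [inclusive]".

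SAP 4.7.2.2.2 (Open-Label Extension, Falls) puts these windows to use. Of both variables it states: "occurring from Week 25 up to Week 48 inclusive will be summarized by treatment, including separate summaries for subintervals". The windows it points to are those of SAP 4.7.1.2.

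SAP 4.7.2.2.3 (Falls) confirms the length of the open-label phase for the 12-month model, with the words "period covers Weeks 25 to 48".

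Neither document gives a reason for a 4-week final window, and SAP Section 5 (modifications from the protocol) does not mention one. Nothing says that window counts are converted to rates.

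**The concern.** Three of the four quarter windows are 12 weeks and the fourth is 4. In the double-blind period the two quarters tile the period exactly. In the open-label period they do not.

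The text is operative. A programmer who follows SAP 4.7.2.2.2 will produce a Weeks 37-40 row or column beside a Weeks 25-36 one, with no summary for Weeks 41-48.

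Both variables are raw counts, so nothing corrects for window length. A reader who scans across the windows would see fewer falls, and fewer patients falling, in the last window even if nothing had changed. Comparing windows is a natural way to read the table. SAP 4.7.2.3 itself defines a responder by the change in falls between two windows, although it uses the two equal double-blind ones. What is at stake is the reading of one descriptive open-label table.

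**Working it through.** **Inputs.** Window limits are from SAP 4.7.1.2. The open-label period is from SAP 4.7.1.2, 4.7.2.2.2 and 4.7.2.2.3. The fall rate is not in the documents. It is assumed below to range from 0.25 to 4 falls per patient per 12 weeks, constant over time and Poisson, with the same patients under observation throughout.

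**1. Window lengths** (last week − first week + 1):

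| Window | Length |
|---|---|
| Weeks 1-12 | 12 |
| Weeks 13-24 | 12 |
| Weeks 25-36 | 12 |
| Weeks 37-40 | 4 |

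**2. Do the quarters cover their period?**

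- Double-blind: 12 + 12 = 24 weeks, which matches Weeks 1-24.
- Open-label as written: 12 + 4 = 16 weeks against 24 for Weeks 25-48.
- Uncovered: 24 − 16 = 8 weeks (Weeks 41-48), which is 8/24 = 33% of the open-label period. Over the whole 48 weeks the quarters cover 40.
- With a last window of Weeks 37-48: 12 + 12 = 24, which matches.

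**3. Does observation stop at Week 40?** Counted from Day 1, Week 40 ends on Day 40 × 7 = 280 and Week 48 on Day 48 × 7 = 336. The Part 2 schedule (protocol Table 6) has dosing to Day 337 and an end-of-treatment visit at Day 358, and the activity device is to be worn for the whole study. Data for Weeks 41-48 are therefore planned.

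**4. Effect on the number of falls.** At a constant rate the expected count is proportional to window length: 4/12 = 33% of the preceding window, or 67% lower with no true change. The true rate would have to triple for the two raw counts to be equal.

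**5. Effect on the number of patients who fell.** P(at least one fall) = 1 − exp(−r) over 12 weeks and 1 − exp(−r/3) over 4 weeks, with r the assumed falls per patient per 12 weeks:

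| r | 12 weeks | 4 weeks | Relative drop |
|---|---|---|---|
| 0.25 | 22.1% | 8.0% | 64% |
| 0.5 | 39.3% | 15.4% | 61% |
| 1 | 63.2% | 28.3% | 55% |
| 2 | 86.5% | 48.7% | 44% |
| 4 | 98.2% | 73.6% | 25% |

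The drop on this variable thus depends heavily on a rate that nobody has stated.

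**6. Which falls analyses use Weeks 37-40?**

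| Analysis | Weeks used |
|---|---|
| Double-blind Andersen-Gill model (4.7.2.2.1) | 1-24 |
| 12-month Andersen-Gill model (4.7.2.2.3) | 1-24 and 25-48 |
| Falls responder criterion, Fisher's exact test (4.7.2.3) | 1-12 and 13-24 |
| Falls subgroup analyses (4.9) | Double-blind period |
| Open-label descriptive summary (4.7.2.2.2) | 25-48 and its subintervals, including 37-40 |

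Only the last one is affected.

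**The case against.** The strongest reply is that little follows from the short window. Falls are an exploratory endpoint, the table is descriptive, and no test or estimate draws on Weeks 37-40. If rows are labelled as the SAP defines them, the short window is visible, and the Weeks 25-48 total will usually exceed the sum of the two parts. All of that stands, and it sets the size of the point. It does not make the window right: the summary is still planned, and it still omits a third of the period.

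Several stronger readings are tempting, and the documents do not support them:

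- **Data from Weeks 41-48 are lost.** They are not. They remain in the Weeks 25-48 and 1-48 totals, in the 12-month model and in the individual listings. For the number of falls, the Weeks 41-48 count can be recovered by subtraction. For patients who fell it cannot be recovered from the summary, because one patient can fall in several windows.
- **A claim of fewer falls over 12 months on ACE-083 could rest on this.** No planned analysis would produce such a claim from this window, and patients in the placebo-first sequence receive placebo in Weeks 1-24, so 12 months on ACE-083 is untrue for them.
- **The comparison of treatment sequences is biased.** Both sequences have the same 4-week window. The comparison within it is only thinner, with a third of the exposure.
- **The 67% figure, and the requirement that the parts sum to the total, apply to both lists.** They apply only to the number of falls. Counts of patients who fell need not add up across windows, even with correct limits.

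It can also be said that the sponsor may have meant 4 weeks, since falls are listed in 4-week intervals. That describes how falls are recorded. It does not explain why one interval stands in for a quarter. Intent cannot be proved either way, so the fix allows for both.

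**Conclusion.** The entry is wrong as written, or at least unexplained, in both falls lists. The final open-label window is 4 weeks instead of 12, and 8 of 24 open-label weeks are in no subinterval. At a constant fall rate, with the same patients observed, the raw number of falls in it would be about 33% of the preceding window's. The number of patients who fell would be lower too, by 25% to 64% over the range of rates assumed here.

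The week counts rest on the SAP alone and are certain. The size of the apparent drop rests on the constant-rate assumption and, for patients who fell, on a Poisson model with assumed rates. That Weeks 37-48 was meant is an inference from the 12-week pattern and the 24-week total.

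The consequence is minor. It is confined to a descriptive summary of an exploratory endpoint, and no hypothesis test, model estimate or between-sequence comparison is put in doubt.

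**What to change.** In SAP 4.7.1.2, change the Weeks 37-40 entry to Weeks 37 to 48 inclusive, once under the number of falls and once under the number of patients who fell. All four quarters are then 12 weeks, and for the number of falls the two open-label quarters sum to the Weeks 25-48 total.

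If the 4-week window was intended, say so and why, add a window for Weeks 41-48, and report falls per person-time so that windows of different length can be compared.

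The cost is two line edits, plus any output template already built from this list. No data collection, model or sample size changes. It is best done before database lock.

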### **Activity Level (Part 2 double-blind and open-label)**

Activity level is defined as the average number of steps per day as measured by the PAMSys™ device over the patient's study participation, adjusted for overall compliance in using the device to record such activity.

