- Percent and absolute change from baseline in biomarkers

Part 2

Primary:

• Percent change from baseline in muscle volume of injected muscle by MRI

Secondary:

- Percent and absolute change from baseline in intramuscular fat fraction of the injected muscle by MRI
- Percent change from baseline in strength measurements by maximum voluntary isometric contraction of ankle dorsiflexion measured by quantitative muscle testing
- Percent change from baseline in functional assessments: 10-meter walk/run, 6-minute walk test, Berg balance scale
- Percent and absolute change from baseline in CMTES2 and CMT-HI
- Presence and nature of AEs including injection site reactions and changes in clinical laboratory parameters
- Pharmacokinetic parameters for ACE-083 serum concentrations over time

Exploratory:

- Percent and absolute change from baseline in biomarkers
- Percent and absolute change from baseline in TA CMAP amplitude
- Percent and absolute change from baseline in gait parameters
- Activity level and falls (PamSysTM wearable device)
- Percent change from baseline in the 100-meter timed test

Methodology

This is a multicenter, phase 2 study to evaluate the safety, tolerability, pharmacodynamics (PD), efficacy, and PK of ACE-083 in patients with CMT1 and CMTX, to be conducted in two parts. Part 1 is non-randomized, open-label, dose-escalation and Part 2 is randomized, double-blind, and

placebo-controlled. Patients who have signed the informed consent form (ICF) and meet the eligibility criteria will be enrolled into the study.

Study Design

Part 1: N=Up to 18 (non-randomized, open-label, dose-escalation)

Cohort	ACE-083 Dose per Muscle ^a	ACE-083 n
1	150 mg	6
2	TBD up to 200 mg ^b	6
3	TBD up to 250 mg ^b	6

Part 2: N=Up to 40 (6-month, randomized, double-blind, placebo-controlled, with 6-month open-label extension)

	6-month placebo controlled		6-month open-label extension
ACE-083 Dose per Muscle ^a	ACE-083 n	Placebo n	ACE-083 n
TBD up to 250 mg ^b	20	20	40

^a Administered bilaterally by injection into the tibialis anterior muscle once every 3 weeks

^b Dose level to be based on recommendations from the Safety Review Team (SRT)

Part 1 (non-randomized, open-label, dose-escalation)

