¹⁵ MRI assessments should be completed within 5 days prior to the scheduled dose administration, with the exception of the Day 1 MRI which may be completed within 14 days prior to Day 1 visit. MRI assessments during the follow-up period (Day 358/ET and Day 393/EOS) have a ± 5 day window.

¹⁶ 10-meter walk/run, 6-minute walk, 100-meter timed test (Part 2, open-label only; starting at the Dose 10 visit and continuing through to the EOS visit at all timepoints noted). Tests may be performed within 3 days prior to Day 1 visit.

¹⁷ Gait parameters, Berg balance scale. Tests may be performed within 3 days prior to Day 1 visit.

¹⁸ Maximum voluntary isometric contraction testing will be conducted using a handheld dynamometer. Both sides will be tested (right and left).

¹⁹ CMTES2 to be assessed by investigator; CMT-HI to be completed by patient

²⁰ Randomization should occur within 24 hours prior to Day 1 dose.

²¹ PamSysTM device is a physical activity monitoring system that will be worn by the patient for the duration of the study.

²² Study drug administration should occur within 21 days (\pm 3 days) of the previous dose.

²³ If subjects enroll directly into a separate extension study and will receive additional treatment with ACE-083, they do not need to complete the EOS visit. For these subjects, their final Study Visit in this protocol will be the ET visit.

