#### **Part 2**

- To evaluate changes in biomarkers
- To evaluate changes in tibialis anterior (TA) compound muscle action potential (CMAP)
- To evaluate changes in gait, activity level, and fall parameters
- To evaluate changes in motor function via the 100-meter timed test

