### **Activity Level**

Individual data will be listed.

Exploratory analyses may be performed as appropriate.

No imputations will be performed for missing data.

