## **4.9. Subgroup Analyses**

Subgroup analyses will be performed for selected efficacy and pharmacodynamics data from the double-blind period of Part 2.

Subgroups consist of the following:

- Ankle Dorsiflexion MRC-MMT Grade {weaker of two sides at Screening}: (3 to 4-; 4 to 4+)
- Ankle Dorsiflexion Screening MRC-MMT Grade of 4- to 4+ on both left and right sides
- Plantar Flexion MRC-MMT Grade {weaker of two sides at Screening}: (4- to 4+; 5- to 5)
- Knee Extension MRC-MMT Grade {weaker of two sides at Screening}: (3+ to 4+; 5- to 5)
- MRC-MMT Grade {weaker of two sides at Screening} for plantar flexion and knee extension
  - Levels are “Both 5- to 5” and “Not both 5- to 5”.
  - “Both 5- to 5” means that the MRC-MMT grade {weaker of two sides} for both plantar flexion and knee extension must both be between 5- and 5.

- “Not both 5- to 5+” means that the MRC-MMT grade {weaker of two sides} for any or both plantar flexion and knee extension should not both be between 5- and 5+. For example, a patient with plantar flexion MRC-MMT grade {weaker of two sides} of a 5- and knee extension MRC-MMT grade {weaker of two sides} of 4 would be classified as “Not both 5- to 5+”.
- Baseline Fat Fraction (%): (< median;  $\geq$  median)
- CMT type: (CMT1, CMTX)
- CMT gene mutation: (CMT1A, not CMT1A)
- Usage of Braces (Yes; No)
  - This information is contained in the individual patient’s CMT disease history
- Dose per Calculated Contractile Muscle Mass (mg/g): (< median;  $\geq$  median)
- Exercise Program: (resistance; no resistance)
  - The “resistance” subgroup includes patients who responded “Yes” to the question “Does the patient have a regular (at least once a week) exercise program?” and reported “Resistance training” as a type of exercise program.
  - The “no resistance” subgroup includes patients who responded “Yes” to the question “Does the patient have a regular (at least once a week) exercise program?” and did not report “Resistance training” as a type of exercise program.
- Baseline CMT-HI Total Score: (< median;  $\geq$  median)
- Activity level (steps/d): (< median;  $\geq$  median)
  - This is defined as the average number of steps per day as measured by the PAMSys™ device over the patient’s study participation in the Part 2 double-blind period, adjusted for overall compliance in using the device to record such activity.
- ADA (ADA +; ADA-)

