 PK samples on dosing day have a ±15 minute window for post-dose sample collection. Pre-dose samples may be collected up to 4 hours prior to dosing.

 ECG is to be conducted within 1 hour of the 4h PK sample.

 MRI assessments should be completed within 5 days prior to the scheduled dose administration, with the exception of the Day 1 MRI which may be completed within 14 days prior to Day 1 visit. MRI assessments during the follow-up period (Day 358/ET and Day 393/EOS) have a ± 5 day window.

 10-meter walk/run, 6-minute walk. Tests may be performed within 3 days prior to Day 1 visit.

 Gait parameters, Berg balance scale. Tests may be performed within 3 days prior to Day 1 visit.

 Maximum voluntary isometric contraction testing will be conducted using a handheld dynamometer. Both sides will be tested (right and left).

 CMTES2 to be assessed by investigator; CMT-HI to be completed by patient

 Randomization should occur within 24 hours of Day 1 dose.

 PAMSys™ device is a physical activity monitoring system that will be worn by the patient for the duration of the study.

 Study drug administration should occur within 21 days (± 3 days) of the previous dose.

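### Activity level is defined as one step average over the whole study, which pools blinded and open-label time, gives no change score, and conflicts with SAP 4.9, where on-treatment steps also form a subgroup.

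*SAP*

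**What the plan says.** The Part 2 exploratory objective in SAP 2.3 is "To evaluate changes in gait, activity level, and fall parameters". SAP 4.7.1.2, under a heading naming both the double-blind and open-label periods, gives the variable: "Activity level is defined as the average number of steps per day as measured by the PAMSys™ device over the patient's study participation", adjusted for compliance with the device. It sets no period, baseline window or change score.

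SAP 4.9 uses the same term for a median-split subgroup but takes the average "over the patient’s study participation in the Part 2 double-blind period, adjusted for overall compliance".

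Falls, listed just before activity level in SAP 4.7.1.2 and tied to the same device, are broken into week intervals. For the comparison of the two periods, falls are assigned to Weeks 1-24 (double-blind) and Weeks 25-48 (open-label).

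The protocol's schedule of events (Appendix 1, Table 6) has the device handed out at screening, Day -28 to Day -7. Footnote 21 says that the "device is a physical activity monitoring system that will be worn by the patient for the duration of the study". From Day 190 both arms receive ACE-083 (SAP 3.2; Appendix 1).

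For analysis, the Activity Level entries in SAP 4.7.2.2 offer listings and this: "Exploratory analyses may be performed as appropriate". The protocol synopsis words the Part 2 exploratory endpoint as "Activity level and falls (PamSysTM wearable device", without the change-from-baseline wording that it gives gait and biomarkers.

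**The concern.** A single average over the whole of a patient's participation has no before and after, so it cannot show a change. For a placebo patient who completes the study, it is also roughly half placebo time and half active-drug time. A placebo patient who leaves before Day 190 contributes blinded time only, so the treatment mix differs between patients within the same arm.

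The definition is almost all that the SAP fixes in advance about this endpoint. If it is followed as written, later exploratory work starts from a variable that does not isolate the randomised comparison.

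The subgroup use matters more directly, because it feeds a planned analysis. SAP 4.9 estimates and tests the treatment effect at two-sided 0.10 within each subgroup category for 15 parameters, including total muscle volume, 6MWD and falls. Steps taken on treatment are themselves a trial outcome. If ACE-083 changes walking activity, the patients above the median in the two arms are no longer comparable groups.

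**Working it through.** The documents give no effect size, SD, power or sample size for steps, so there is no stated figure to reproduce. The check compares the definitions and then sizes the dilution.

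**Definitions side by side**

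- SAP 2.3 asks about changes. SAP 4.7.1.2 supplies one value per patient. The general baseline rule in SAP 4.1.4 (the last value available before first dosing) cannot be applied to a whole-study mean.
- SAP 4.7.1.2 averages over all participation; SAP 4.9 averages over the double-blind period only. The same term has two windows.

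**Inputs for the dilution (Protocol Appendix 1, Table 6)**

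- Double-blind: Day 1 to Day 189 = 189 days.
- Open-label: Day 190 to Day 357 = 168 days; 189 + 168 = 357.
- Follow-up, if counted: Day 358 to Day 392 = 35 days; 357 + 35 = 392.
- Screening wear, if counted: 7 to 28 days, at most 28/420 = 6.7% of the window.

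**Formula**

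Let f(d) be the effect on steps d days after the first active dose, as a fraction of the full effect. The first active dose is Day 1 in one sequence and Day 190 in the other. The contrast over a window is the mean over its days of f(day - 1) - f(day - 190), with f = 0 before active dosing. The retained fraction is the whole-participation contrast divided by the double-blind contrast. The shapes of f are assumptions.

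**Immediate constant effect.** The double-blind contrast is 1 and the whole-window contrast is 189/N, where N is the number of days averaged: 189/357 = 0.529 at one end and 189/420 = 0.450 at the other. In the calendar weeks used for falls, 24/48 = 0.50.

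**Linear onset.** With a 6-week (42-day) onset the double-blind contrast is (20.5 + 147)/189 = 0.886. With 12 weeks (84 days) it is (41.5 + 105)/189 = 0.775. In both cases the whole-window contrast is still 189/N, because each arm reaches the full effect before the window ends. So the retained fraction for 6 weeks is 0.529/0.886 = 0.597 down to 0.450/0.886 = 0.508. With a 27-week (189-day) onset the double-blind contrast is only 94/189 = 0.497.

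| Days averaged | N | Immediate | 6-week | 12-week | 27-week | Still growing (d/189, no ceiling) |
|---|---|---|---|---|---|---|
| Day 1-357 | 357 | 0.529 | 0.597 | 0.683 | 1.058 | 1.476 |
| Day 1-392 | 392 | 0.482 | 0.544 | 0.622 | 0.969 | 1.523 |
| 7 screening days + 357 | 364 | 0.519 | 0.586 | 0.670 | 1.037 | 1.447 |
| 7 screening days + 392 | 399 | 0.474 | 0.534 | 0.611 | 0.952 | 1.497 |
| 28 screening days + 357 | 385 | 0.491 | 0.554 | 0.633 | 0.981 | 1.368 |
| 28 screening days + 392 | 420 | 0.450 | 0.508 | 0.581 | 0.905 | 1.422 |

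A double-blind-only average has a retained fraction of 1.00 by construction. The table applies to patients who complete the window. Those who leave before Day 190 add no open-label time, and those who enter the extension study need no Day 393 visit (Table 6, footnote 23).

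**Subgroup.** The SAP 4.9 average starts after randomisation, so the median split depends on what happened on treatment. If ACE-083 raises steps, the upper half contains ACE-083 patients who would have been below the median untreated, set against placebo patients who were active without the drug. The documents give no figure from which to size this bias.

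**The case against.** The strongest reply is that nothing planned depends on the whole-study average. The SAP specifies no model, arm comparison or test for activity level. The protocol endpoint is the level itself, so the SAP 4.7.1.2 wording fits that endpoint; the mismatch is with the word for change in an exploratory objective shared by gait, activity and falls. The raw data allow period means, and SAP 4.9 already restricts its average to the double-blind period. Subgroup findings are labelled hypothesis-generating, without type I error control.

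Most of this stands and limits the weight of the point. It also rules out four stronger readings that a reader might infer:

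- That any arm contrast would be halved. This needs an effect that is immediate, constant, and equal in both arms once both are on drug. The documents give no onset for steps. The drug is meant to act by building muscle over repeated three-weekly doses, so a slower onset is plausible, and the loss then shrinks or disappears.
- That a change in activity cannot be derived at all. It cannot be derived from the variable as defined. It can be derived from the device data once windows are set.
- That a planned test of steps is biased. None is planned.
- That screening days are certainly in the average. SAP 4.7.1.2 does not say when participation starts. Their inclusion is an inference from distribution at screening and wear throughout.

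The reply does not remove the conflict between SAP 4.7.1.2 and 4.9, nor the pooling of treatments in a variable defined in advance. Nor does it answer the subgroup point: a hypothesis-generating label does not restore comparability within strata formed after randomisation.

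**Conclusion.** The point holds as a minor one. The whole-participation definition pools double-blind and open-label time, gives no change score for its objective, and disagrees with SAP 4.9. An arm contrast built on it would compare ACE-083 followed by ACE-083 with placebo followed by ACE-083. Relative to the double-blind contrast it would keep 0.45-0.53 of an immediate constant effect, 0.51-0.60 with a 6-week linear onset, 0.58-0.68 with 12 weeks and 0.91-1.06 with 27 weeks. It would be larger (1.37-1.52) if the effect kept growing. These figures assume completion of the window, even wear and the stated onset shapes. The practical lesson is that the treatment mix makes the contrast hard to interpret, whichever way its size moves.

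Separately, the SAP 4.9 activity subgroup conditions on a post-randomisation outcome in an analysis that is planned, although a pre-dose value should be available. Bias arises there to the extent that treatment affects steps. The activity endpoint is exploratory and no primary or secondary analysis rests on it, apart from the subgroup estimates.

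**What to change.** In SAP 4.7.1.2, define compliance-adjusted mean steps per day separately for a pre-dose (screening) window, the double-blind period and the open-label period, using the Weeks 1-24 and 25-48 split already applied to falls. State how the compliance adjustment is made and the minimum wear required. Define change as the double-blind value minus the pre-dose value. Base any exploratory arm comparison on the double-blind value with the pre-dose value as baseline, and summarise the open-label value by sequence.

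One detail needs settling. Counted from Day 1, Week 24 ends on Day 168 (24 x 7), whereas open-label dosing starts on Day 190, after 189/7 = 27 weeks. Weeks 1-24 are therefore wholly blinded, but Weeks 25-27 are blinded time inside the nominal open-label window. The SAP should say how those three weeks are treated.

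Align 4.7.1.2 with 4.9 so that the term has one meaning, and form the 4.9 activity subgroup from the pre-dose value.

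The cost is SAP wording and derivation code, with no new data collection. The downside is a short pre-dose window of about 7 to 28 days, so the baseline is noisier. With no imputation planned for this variable, patients without screening wear drop out of the baseline-adjusted analysis and the subgroup.
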